## 4 STUDY DESIGN

### 4.1 Overall design

This Phase 1 study is a randomized, participant-blind, investigator-blind, placebo-controlled safety/tolerability, PK, and PD evaluation of a [REDACTED] rozanolixizumab SC dose administered to healthy participants by either a programmed syringe driver or by MP via self-administration. As rozanolixizumab has not been administered SC to humans by MP, this study represents a preliminary assessment of the MP method prior to recommendation of this administration technique in the clinical dosing of rozanolixizumab.

Participants will be divided into 2 body weight categories:  $\geq 35$  to  $< 50$ kg and  $\geq 50$ kg. Within the higher body weight category, 16 participants will be randomly allocated to syringe driver or MP cohorts and, subsequently, to rozanolixizumab (6 participants total) or placebo (2 participants total) (Figure 1-1). Participants of lighter body weights between  $\geq 35$  to  $< 50$ kg are being investigated to a) support the newly recommended rozanolixizumab dosing with a fixed dose of [REDACTED] in adults of  $\geq 35$ kg to 50kg (via syringe driver administration) and (b) to assess the MP method for a [REDACTED] IMP volume.

Within the lower body weight category, the allocation to either syringe driver or MP will be determined by order of recruitment rather than randomization. The first 8 participants will be allocated to the syringe driver cohort and randomly allocated to receive either rozanolixizumab [REDACTED] (6 participants total) or placebo (2 participants total). The subsequent 8 participants will be allocated to the MP cohort and randomly allocated to receive either rozanolixizumab [REDACTED] (6 participants total) or placebo (2 participants total).

The treatment groups are planned to be as follows:

- Cohort 1 (participants with a body weight of  $\geq 35$ kg to  $< 50$ kg) is planned to have 6 participants receive rozanolixizumab [REDACTED] and 2 participants receive placebo via syringe driver at a [REDACTED].
- Cohort 2 (participants with a body weight of  $\geq 35$ kg to  $< 50$ kg) is planned to have 6 participants receive rozanolixizumab [REDACTED] and 2 participants receive placebo via MP through self-administration at a [REDACTED].
- Cohort 3 (participants with a body weight of  $\geq 50$ kg) is planned to have 6 participants receive rozanolixizumab [REDACTED] and 2 participants receive placebo via syringe driver at a [REDACTED].

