## 7.2 Participant discontinuation/withdrawal from the study

Participants are free to withdraw from the study at any time, without prejudice to their continued care. The study is designed to collect data on 24 participants that receive rozanolixizumab (6 per cohort). If study participants discontinue before the end of the safety evaluation period, replacement participants may be considered at the discretion of the sponsor, depending on how the discontinuation affects the study's ability to collect sufficient data to support the study

objectives. For each case of participant discontinuation, the decision on whether to recruit a replacement and the reason behind the decision will be documented.

If the participant withdraws consent for disclosure of future information, the sponsor may retain and continue to use any data collected before such a withdrawal of consent.

If a participant withdraws from the study, he/she may request destruction of any samples taken and not tested, and the investigator must document this in the site study records. Participants who withdraw from the study will be encouraged to return to the clinic to complete the Withdrawal Visit (see [Table 1-1](#)).

See [Table 1-1](#) for data to be collected at the time of study discontinuation and follow-up and for any further evaluations that need to be completed.

Participants should be withdrawn from the study if any of the following events occur:

1. Participant develops an illness that would interfere with his/her continued participation.
2. Participant is noncompliant with the study procedures or medications in the opinion of the investigator.
3. Participant takes prohibited concomitant medications as defined in this protocol that might interfere with the outcome of the study or might be an increased risk to the study participant.
4. Participant withdraws his/her consent.
5. There is confirmation of a pregnancy during the study, as evidenced by a positive pregnancy test.
6. The sponsor or a regulatory agency requests withdrawal of the participant.

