#### **9.4.2 PK analyses**

Pharmacokinetics will be determined by non-compartmental analysis in Phoenix (Certara, USA) using the PK Per Protocol Set.

For calculation of the plasma PK parameters of rozanolixizumab, the actual sampling time points will be used in order to evaluate the PK parameters.

The plasma concentration-time profiles and PK parameters of rozanolixizumab will be summarized by method, body weight, and dose level using descriptive statistics (number of available observations, arithmetic mean, standard deviation, the geometric mean, the coefficient of variation of the geometric mean, median, minimum, and maximum). Values below the lower limit of quantification (LLOQ) will be reported with a clear sign indicating that they were below the LLOQ. Descriptive statistics of concentrations will be calculated if at least two-thirds of the individual data points are quantifiable ( $\geq$ LLOQ).

Individual concentration time profiles will be displayed graphically on a linear-linear scale and semi-logarithmic scale. Geometric mean plasma concentrations-time curves including 95% confidence intervals will be displayed by method, body weight, and dose level.

The comparability of dose-adjusted PK parameters ( $C_{\max}/D$  and  $AUC_{(0-t)}/D$ ) between the methods (MP and the syringe driver) will be assessed within an analysis of variance model with Method (MP vs syringe driver) as a main effect.

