4 POPULATIONS FOR ANALYSIS

Enrolled Set: The Enrolled Set (ES) will consist of all study participants who have signed the Informed Consent Form (ICF).

Randomized Set: The Randomized Set (RS) consist of all enrolled study participants who were randomized.

Safety Analysis Set (SS): All randomized study participants who received IMP. Analysis of this set will be according to the treatment the study participants actually received and will be used for the demographic and safety analyses.

Pharmacokinetic (PK) Per Protocol Set (PK-PPS): All study participants that received active study medication and had at least 1 observable PK measurement and had no important protocol deviations affecting the PK parameters. If a study participant in the PK-PPS is missing individual time points or are otherwise unobservable, they will be included in the PK-PPS but those time points will be omitted from the PK summaries, as appropriate.

Pharmacodynamic (PD) Per Protocol Set (PD-PPS): The PD-PPS is a subset of the SS, consisting of those study participants who had no important protocol deviations affecting the PD variables, as confirmed during a pre-analysis review of the data prior to database lock.

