5.1.1.3 Treatment assignment and treatment groups

Treatment assignment for the SS, PK-PPS and PD-PPS will be according to the actual treatment received. Listings and summaries will be presented by cohort and treatment group.

The following label conventions and order will be used in the TFLs (except for PK analysis)

- Cohort 1 - ≥ 35 kg to < 50 kg, Syringe driver
 - Placebo via Syringe Driver
 - Rozanolixizumab [REDACTED] Syringe Driver
- Cohort 2 - ≥ 35 kg to < 50 kg, MP

-
- Placebo via MP
 - Rozanolixizumab [REDACTED] MP
 - Cohort 3 ≥ 50 kg, Syringe driver
 - Placebo via Syringe Driver
 - Rozanolixizumab [REDACTED] Syringe Driver
 - Cohort 4 ≥ 50 kg, MP
 - Placebo via MP
 - Rozanolixizumab [REDACTED] MP
 - Syringe Driver, All Participants
 - Placebo
 - Rozanolixizumab
 - MP, All Participants
 - Placebo
 - Rozanolixizumab

The following label conventions and order will be used in the PK TFLs:

- Rozanolixizumab via Syringe Driver, All
- Rozanolixizumab via MP, All

The explanatory description of each cohort may be dropped from the labels if space is limited. For listings, the cohort description and the treatment name will be written out in full.

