5.4.1.2 Main analytical approach

PK analyses

All PK summaries will be done using PK-PPS and displayed by method of administration (see [section 5.1.1.3](#)). The plasma concentration-time profiles and PK parameters of rozanolixizumab (C_{max} , AUC, and T_{max}) will be summarized by method, dose and body weight for rozanolixizumab treated patients using descriptive statistics (number of available observations, arithmetic mean, standard deviation, the geometric mean, the coefficient of variation of the geometric mean, median, minimum, and maximum). For t_{max} , only median, minimum and maximum will be reported. Values below LLOQ will be reported with a clear sign indicating that they were below the LLOQ. Descriptive statistics of concentrations will be calculated if at least two-thirds of the individual data points are quantifiable (\geq LLOQ).

Individual and spaghetti concentration time profiles will be displayed graphically on a linear-linear scale and semi-logarithmic scale. Geometric mean plasma concentrations-time curves including 95% CI will be displayed.

The comparability of dose-adjusted PK parameters (C_{max}/D and $AUC_{(0-t)}/D$) between the methods (MP and the syringe driver) will be assessed within an analysis of variance (ANOVA) model with method (MP vs syringe driver) as a main effect, with no additional covariates. The log-transformed PK parameters will be used in the ANOVA model. The model structure to be used is therefore

$$\log(\text{Parameter}) \sim \text{Method of Administration}$$

This model structure has been chosen to reflect the intended dosing scheme of fixed dosing (e.g., of ██████) applied to adults >35 kg irrespective of weight. This will thus allow us to draw conclusions about the presence or absence of effects of the method of dose administration on parameter values when given using the intended scheme. Any potential effect of weight on parameter values will be accounted for by the study design itself by the balanced proportion of lower weight/higher weight participants receiving their dose using each of MP and Syringe driver.

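### Balance by weight category protects the MP/syringe driver PK ratio but not its 90% CI, so the one-factor ANOVA can report needlessly wide intervals

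*SAP*

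**What the plan says.** SAP 5.4.1.2 (PK analyses) assesses C_max/D and AUC(0-t)/D in an ANOVA of the log-transformed parameter with "method (MP vs syringe driver) as a main effect, with no additional covariates". It reports the geometric least square mean ratio (GLSMR), MP over syringe driver, with a 90% CI. The reason given for leaving weight out is this: "effect of weight on parameter values will be accounted for by the study design itself by the balanced proportion of lower weight/higher weight". Protocol 9.4.2 specifies "an analysis of variance model with Method (MP vs syringe driver) as a main effect"; it does not say that other terms are excluded.

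Protocol 7.2 plans 24 participants on rozanolixizumab, 6 per cohort. Each method therefore has 6 active participants at 35 to <50 kg and 6 at 50 kg or more. The analysis uses the PK Per Protocol Set, which SAP section 4 limits to participants on active drug who "had at least 1 observable PK measurement and had no important protocol deviations affecting the PK parameters". On replacement, Protocol 7.2 says: "If study participants discontinue before the end of the safety evaluation period, replacement participants may be considered at the discretion of the sponsor".

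**The concern.** The rationale treats two things as one. Equal numbers per cell remove a weight-category effect from the difference between methods. They do not remove it from the residual mean square that sets the width of the CI. If exposure per unit dose differs between the categories, that known design difference is counted as random error and the interval is wider than the data warrant.

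Balance in the analysis set is not assured either. Exclusions for important PK deviations can fall unevenly across cells. Replacement is at the sponsor's discretion and is tied to discontinuation, so it need not restore the cells. With unequal cells the one-factor estimate also picks up part of the weight effect.

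At stake is the precision of the only planned model-based PK comparison of the two methods, at 12 versus 12. A second cost is a sentence telling readers that weight has been dealt with when only the point estimate is protected. No weight-adjusted model is planned elsewhere: SAP 5.4.2 plans no supportive secondary analysis and SAP 5.8 no subgroup analysis.

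**Working it through.** **Plan's own figure.** The plan states no CI width, SD or weight effect, so there is nothing to reproduce beyond 4 × 6 = 24 active participants.

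**Inputs from the documents.** 6 active participants per weight-by-method cell (Protocol 7.2, SAP 1.2); log scale, method only, 90% CI (SAP 5.4.1.2).

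**Assumed inputs.** Low/high-weight ratio of dose-adjusted exposure 1.0 to 2.0; within-cell CV 30% to 60%; weight effect the same under both methods; no true method effect.

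**Formula.** Let δ = ln(ratio) and σ² = ln(1 + CV²). The weight sum of squares (1 df) has expectation σ² + 24δ²/4 = σ² + 6δ². The one-factor model pools it with the other 21 residual df:

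E[MSE] = (21σ² + σ² + 6δ²)/22 = σ² + 6δ²/22.

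The true variance of the method difference stays at 2σ²/12. The approximate log-scale width of the planned CI, relative to a model with method and weight category, is

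√(1 + 6δ²/(22σ²)) × t(0.95; 22)/t(0.95; 21), with t values 1.7171 and 1.7207.

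**Worked case, ratio 1.67 and CV 40%.** δ = 0.513, σ² = ln(1.16) = 0.148. The width ratio is √(1 + 0.0717/0.1484) × 0.998 = 1.215. Simulation gives 1.217, from mean log widths of 0.651 and 0.535. For an observed GLSMR of 1 these are exp(±0.3255) = 0.722 to 1.385 as planned, and exp(±0.2675) = 0.765 to 1.307 with weight fitted.

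**Simulation, 100,000 trials per setting.** Entries are coverage of the planned 90% CI / its log-scale width relative to the two-factor CI.

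| Low/high ratio | CV 30% | CV 40% | CV 60% |
|---|---|---|---|
| 1.0 | 0.901 / 0.998 | 0.899 / 0.998 | 0.901 / 0.998 |
| 1.25 | 0.921 / 1.075 | 0.914 / 1.043 | 0.906 / 1.020 |
| 1.5 | 0.955 / 1.232 | 0.939 / 1.140 | 0.920 / 1.069 |
| 1.67 | 0.973 / 1.354 | 0.953 / 1.217 | 0.930 / 1.110 |
| 2.0 | 0.990 / 1.592 | 0.975 / 1.373 | 0.948 / 1.194 |

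With weight category fitted, coverage was 0.899 to 0.901 throughout. The two models gave the same point estimate in every balanced trial.

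**Break-even.** Setting t₂₂²(σ² + 6δ²/22) = t₂₁²σ² gives δ = 0.124σ. The weight term narrows the CI once the ratio exceeds 1.037 (CV 30%), 1.049 (40%) or 1.071 (60%).

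**Unequal cells.** If k low-weight MP participants are lost, the one-factor GLSMR moves from 1 to exp{[(6 − k)/(12 − k) − 0.5]δ}:

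| Participants lost | Ratio 1.25 | Ratio 1.5 | Ratio 2.0 |
|---|---|---|---|
| 1 | 0.990 | 0.982 | 0.969 |
| 2 | 0.978 | 0.960 | 0.933 |

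With the weight term the expected GLSMR stays at 1.00, provided the weight effect is the same under both methods.

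**The case against.** The strongest case against is about importance. The comparison is exploratory (SAP Table 1-1), has no hypothesis test (SAP section 2) and no stated margin, and the error is conservative. All of that stands, and it means no formal conclusion is wrong.

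The size is also assumed. Protocol 4.3 cites simulations showing comparable exposure for a fixed dose and other doses in adults of 35 kg or more. Those simulations compare dosing schemes. They do not show equal dose-adjusted exposure below and above 50 kg, so they do not settle the point in either direction.

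The SAP says its model reflects fixed dosing irrespective of weight. This does not rescue the interval. The weight mix is fixed at half and half under each method, so the spread between categories is not sampling error of the method contrast. With equal cells both models estimate the same ratio.

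A reader could rebuild an adjusted interval from the planned summaries by method, dose and body weight, and the residual plots might show a large split. That helps, but the reported CI stays as it is.

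Three limits stand:

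- A two-level term removes only the difference between categories, not weight variation within them.
- In the lower category "the allocation to either syringe driver or MP will be determined by order of recruitment rather than randomization", so that part of the contrast is not randomized, whatever the model.
- Doses are redacted. If the two low-weight cohorts differ in dose and exposure is not dose-proportional, neither model corrects for it.

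Finally, Protocol 9.4.3 makes the PD ANCOVA analogous to the PK model. A weight term there was not evaluated.

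**Conclusion.** The concern holds. Balance protects the GLSMR, not its CI. The existence and direction of the effect follow from the design. Its size depends on the weight effect relative to the within-cell SD, which the documents do not give: nil if weight category has no effect, 2-7% excess log-scale width at a ratio of 1.25, and up to 59% at a ratio of 2.0 with CV 30%. The shift from one or two lost participants is small beside the width of the CI, but the rationale would then fail for the estimate as well. This is a worthwhile, inexpensive improvement to an exploratory analysis. It does not threaten the study's conclusions.

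**What to change.** - Fit log(Parameter) ~ Method + weight category (<50 kg, ≥50 kg) for C_max/D and AUC(0-t)/D. The method-only model can stay as a supporting output.
- Reword the rationale: equal cells protect the estimated ratio, and the model term removes between-category variance from the error. Claim no more than that.
- As a side matter, reconcile the PK output labels. In SAP 5.1.1.3, "The following label conventions and order will be used in the PK TFLs" introduces only the two pooled method groups, whereas 5.4.1.2 asks for summaries by method, dose and body weight.

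The cost is one residual degree of freedom (22 to 21) and a CI about 0.2% wider if weight has no effect. With 6 per cell the GLSMR does not change. SAP section 1 requires an amendment when analysis definitions change before database lock, and the change should be noted in SAP 6.2. The exclusion of covariates is stated only in the SAP, so the wording of Protocol 9.4.2 need not change. No change to the PD ANCOVA is requested.

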### **Diagnostic assessments**

34. Presence of hepatitis B surface antigen (HBsAg) at Screening or within 3 months prior to dosing.
35. Positive hepatitis C antibody test result at Screening or within 3 months prior to starting study intervention. NOTE: Participants with positive Hepatitis C antibody due to prior resolved disease can be enrolled if a confirmatory negative hepatitis C ribonucleic acid test is obtained.
36. Positive hepatitis C RNA test result at Screening or within 3 months prior to first dose of study medication. NOTE: Test is optional and participants with negative Hepatitis C antibody test are not required to also undergo Hepatitis C RNA testing.
37. Presence of the hepatitis B core antibody (HBcAb) even if HBsAg is negative.
38. Immunoglobulin G <7g/L or >16g/L at the Screening Visit.
39. Positive pre-study drug/alcohol screen.

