### 9.4.3 PD analyses

Total IgG (observed values, change from Baseline, and percentage change from Baseline) will be listed and summarized for the PD Per Protocol Set. The geometric mean Total IgG concentration with 95% confidence interval will be displayed graphically.

Derived parameters for the Total IgG response curve (AUC, maximum decrease in total plasma IgG, and time to minimum plasma concentration) will be listed and summarized for the PD Per Protocol Set.

The comparability of the total IgG Baseline-corrected  $AUC(IgG)/D$  between MP and the syringe driver will be assessed within an analysis of covariance model analogous to the analysis of variance model used to evaluate the PK parameters described above. The Baseline IgG value will be fitted as a covariate.

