The geometric least square mean (GLSM), GLSM differences and the corresponding 90% CI for the differences (MP [Test] - syringe driver [Reference]) will be calculated for PK parameters (log-transformed C_{max} , AUC_{0-t}). Back-transformed (anti-log) estimates of (GLSM, geometric least square mean ratio (GLSMR) and its 90% CI for the comparisons will be presented. In order to verify the normality assumption of the ANOVA, normal quantile-quantile plots will be used to visually inspect the distribution of residuals, and the potential impact of any deviations will be discussed.

PD analyses

All PD summaries will be done using PD-PPS by treatment group described under [section 5.1.1.3](#). Total IgG (observed values, change from Baseline, and percentage change from Baseline) will be listed and summarized for the PD Per Protocol Set. The geometric mean Total IgG concentration with 95% CI will be displayed graphically.

Derived parameters for the Total IgG response curve (AUC, maximum decrease in total plasma IgG, and time to minimum plasma concentration) will be listed and summarized for the PD Per Protocol Set.

The comparability of the total dose adjusted IgG Baseline-corrected AUC (IgG)/D between MP and the syringe driver will be assessed within an ANCOVA model with Baseline IgG value fitted as a covariate. The least square mean (LSM), LSM differences and the corresponding 95% CI for

the differences will be presented for total IgG. The analysis may be conducted on the log scale if the data exhibits substantial non-normality. In this case, the reason for the log-transformation will be described.

The following contrasts will be presented:

- Rozanolixizumab via Syringe Driver vs Rozanoliximab via MP
- Placebo via Syringe Driver vs Placebo via MP
- Rozanolixizumab via Syringe Driver vs Placebo via Syringe Driver
- Rozanoliximab via MP vs Placebo via MP

Additionally, observed values and change from Baseline in serum IgG concentrations at each scheduled assessment during the In-Clinic and SFU Periods will be summarized descriptively.

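### The PD ANCOVA as listed pools active and placebo participants in one slope and one residual variance, without a check, so its 95% intervals can be mis-sized in either direction; the manual push vs syringe driver contrast should come from active participants only.

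*SAP*

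**What the plan says.** SAP 5.4.1.2 (PD analyses) takes as outcome the "total dose adjusted IgG Baseline-corrected AUC (IgG)/D between MP and the syringe driver" and says that it "will be assessed within an ANCOVA model with Baseline IgG value fitted as a covariate". The output is described as "The least square mean (LSM), LSM differences and the corresponding 95% CI for" the differences. Four contrasts follow: active MP vs active syringe driver, "Placebo via Syringe Driver vs Placebo via MP", "Rozanolixizumab via Syringe Driver vs Placebo via Syringe Driver", and the corresponding active vs placebo contrast for MP. The analysis set is the PD Per Protocol Set, which SAP section 4 defines as a subset of the Safety Analysis Set, so it includes placebo.

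The SAP writes out the PK model but not the PD model. It names no group-specific slope, no group-specific variance and no check of either. The quantile-quantile plots are planned for the PK ANOVA and concern normality. The one PD fallback is a change of scale: "The analysis may be conducted on the log scale if the data exhibits substantial non-normality".

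Protocol 9.4.3 describes the PD model as "analogous to the analysis of variance model used to evaluate the PK parameters described above". The PK model has Method as its only effect, and the PK Per Protocol Set contains active participants only. SAP 6.2 declares one change from the protocol, on how safety results are presented, and says that the other analyses follow the protocol.

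**The concern.** An ordinary ANCOVA that yields all four contrasts estimates one Baseline slope and one residual variance across active and placebo. Neither is likely to be common here.

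- **Slope.** The drug speeds up IgG catabolism. If it removes a fraction of IgG, the baseline-corrected AUC rises with Baseline on active and is roughly flat on placebo. Eligible participants can differ widely at Baseline, since the exclusion is "Immunoglobulin G <7g/L or >16g/L at the Screening Visit".
- **Variance.** Active values carry differences between participants in drug response. Placebo values carry mainly biological and assay noise.

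Placebo supplies 6 of the 28 within-group degrees of freedom (21%) before the covariate is fitted, so it affects the error term for the active contrast. That contrast is the only modelled PD comparison of the two methods. With no hypothesis test planned (SAP section 2), its interval is the inferential result.

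**Working it through.** The plan states no variance, power or interval width for this analysis, so there is no figure of its own to reproduce beyond the head count: 4 × (6 + 2) = 32, of whom 24 are active.

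**Degrees of freedom.** Pooled fit with four groups and one slope: 32 − 5 = 27 (t = 2.052). Active only: 24 − 3 = 21 (t = 2.080). Placebo only: 8 − 3 = 5 (t = 2.571).

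**Unequal variance alone.** Let r be the placebo residual SD divided by the active one; r is assumed, because the documents give neither. With the active SD set to 1, the pooled variance is s² = (22 + 6r²)/28. The ratios of model SE to true SE are:

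- active vs active: s
- placebo vs placebo: s/r
- active vs placebo: √[s²(1/12 + 1/4) / (1/12 + r²/4)]

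For r = 0.5, s² = (22 + 1.5)/28 = 0.839 and s = 0.916. The active interval relative to an active-only fit is 0.916 × 2.052/2.080 = 0.904. Coverage is from 20,000 simulated trials per row, with equal slopes.

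| r | Active SE ratio (coverage) | Placebo vs placebo SE ratio (coverage) | Active vs placebo SE ratio (coverage) |
|---|---|---|---|
| 0.25 | 0.89 (92.5%) | 3.58 (about 100%) | 1.64 (99.7%) |
| 0.5 | 0.92 (92.7%) | 1.83 (99.9%) | 1.39 (99.0%) |
| 0.75 | 0.95 (94.2%) | 1.27 (98.4%) | 1.16 (97.4%) |
| 1 | 1.00 (94.9%) | 1.00 (94.9%) | 1.00 (about 95%) |
| 1.5 | 1.13 (97.0%) | 0.75 (86.1%) | 0.81 (about 89%) |

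As r goes to 0, the active interval is at most 12.5% narrower than the active-only one. Above r = 1 every direction reverses.

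**Unequal slope alone** (r = 1; active slope of one residual SD per SD of Baseline, placebo slope 0). The active interval is 6% wider than the active-only one (coverage 95.9%), and the placebo contrasts cover 91% to 92%. The slope therefore works against the variance effect. With r = 0.5 and this slope, coverage is 94.4% (active), 96.7% (placebo vs placebo) and about 96% (active vs placebo).

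**Both together, from the mechanism.** Assumptions: Baseline mean 11.5 g/L, SD 2.0, kept within 7 to 16; the drug removes a mean fraction of IgG over 56 days; one constant D for everyone. The active slope per Baseline SD, in residual SDs, is then about (2.0/11.5)/CV = 0.174/CV, where CV is the between-participant variation in the fraction removed: 0.58 at 30%, 0.87 at 20%, 1.45 at 12%.

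- Reduction 35%, CV 30%, within-participant CV 3%: active SE 26.8 against a true 29.4 (ratio 0.91), coverage 92.6% to 92.8%. Placebo vs placebo 46.4 against 27.1 (1.71; up to 1.75 in repeat runs). Active vs placebo 37.9 against 28.7 (1.32).
- Reduction 15%, CV 20%, within-participant CV 6%: active SE 16.1 against 16.2, so no material error.
- CV about 12%: active coverage 95.7%, and the placebo vs placebo SE ratio falls to 0.86.
- An active-only ANCOVA covered 94.7% to 95.7% in all these settings.

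**Dependence on D.** Placebo has no dose to divide by. In a mid-range setting (reduction 25%, CV 25%, within-participant CV 4.5%), setting placebo D to half the active D gives 96.2% coverage for the active contrast and 91.1% for placebo vs placebo. At one-fifth the figures are 99.3% and 72.4%.

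**The case against.** The SAP does not write a common slope or a common variance. Both are inferred from the phrase that describes the ANCOVA and from the list of contrasts, and Protocol 9.4.3 points to a Method-only model. This stands as a caution about wording. It does not remove the problem, because three of the listed contrasts cannot be produced without placebo in a fit. If placebo drops out because D is undefined, the pooling disappears, but so do those contrasts.

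A reader might infer that the MP vs syringe driver interval is always too narrow and the placebo intervals always too wide. The documents do not support that. They give no IgG AUC variance for either group, and the direction reverses if placebo is the more variable group or if placebo is given a smaller D. It can also change on the permitted log scale, where placebo values near zero become unstable or have no logarithm. Nor can the common slope be cited as a cause of narrowing, since it pushes the other way.

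A reader might also infer that the placebo intervals are useless. With 4 against 4, a placebo-only fit has 5 degrees of freedom, and at r of about 0.75 or more the pooled interval is about as wide as the separate one or narrower. A second model that estimates slopes and variances from 8 placebo participants would be unstable in its own way.

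Finally, the PD comparison is listed as exploratory, there is no margin or test, and Total IgG is also summarised descriptively. That limits the consequence. It does not justify leaving the model unwritten.

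**Conclusion.** The point holds as a gap in specification with a modest numerical effect. The listed contrasts imply that active and placebo share a slope and a variance. The mechanism makes this unlikely and nothing in the SAP checks it, so the 95% intervals may be too narrow or too wide.

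With one constant D, reductions of 15% to 35% and between-participant CVs of about 12% to 30%, the MP vs syringe driver interval runs from up to about 10% too narrow to slightly too wide (coverage 92.6% to 95.7%). The placebo vs placebo SE is 0.86 to 1.75 times its true value. These ranges rest on assumed variances, and a different D for placebo moves them further. The active-only result of about 95% was checked with one active dose, and the dose levels are redacted in the public documents. A claim that the main PD comparison is seriously invalid would go beyond this evidence.

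**What to change.** In SAP 5.4.1.2, write the PD model out as is done for PK. Estimate the rozanolixizumab MP vs syringe driver contrast from active participants only, with Method and Baseline IgG as terms. This is the population of the PK ANOVA and agrees with Protocol 9.4.3.

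Present the placebo vs placebo and active vs placebo contrasts separately, on baseline-corrected AUC not divided by dose. Do so either descriptively or with variances not pooled across active and placebo.

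The cost is a few sentences and a few lines of code. Residual degrees of freedom for the main contrast fall from 27 to 21, which moves the t multiplier from 2.052 to 2.080. If the variances were in fact equal, the loss is about 1.3% of interval width (2.080/2.052 = 1.013).
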